11.3 Blinding

The identity of test and control treatments will not be known to Investigators, Sponsor, research staff, subjects, or the study monitor. The following study procedures will be in place to ensure double-blind administration of study treatments:

- Access to the randomization codes will be strictly controlled by the IRT system.
- Throughout the double-blind study, the blind should remain unbroken except for an emergency when knowledge of the subject's study medication is necessary for further management or if required for regulatory reporting. The Allakos Medical Monitor approves any emergency blind break, if at all possible, prior to the unblinding.

- The lirentelimab and placebo for SC injection will be identical in appearance.
- Results from the analysis of blood samples for PK and ADA will not be provided to the Investigator and Sponsor until after final database lock of the double-blind study.
- Results from the analysis of blood samples for histamine/tryptase tests (collected in case of possible anaphylaxis) will not be provided to the Investigator and Sponsor until after final database lock of the double-blind study, unless required for immediate safety reasons.
- Results of the assessments noted below will not be provided to the Investigator and Sponsor until after final database lock of the double-blind study, so as to not introduce bias. The results will be reviewed on an ongoing basis by the Safety Monitor and escalated as appropriate.
 - Differential cell counts including neutrophils, eosinophils, basophils, monocytes, and lymphocytes.

Other than under the conditions described above, the study blind will be revealed on completion of the study as noted in Section [17.4](#).

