11.4 Breaking the Blind

Breaking the blind in a clinical study on an emergency basis by the site should only occur when knowledge of the treatment to which a subject was allocated would have implications for the emergency medical management of the subject, if required for regulatory reporting, or if there is a pregnancy during the pregnancy reporting period.

If necessary, emergency breaking of the blind can be conducted through the IRT by the Investigator or other registered site users and/or the Medical Monitor. Whenever possible, the Investigator should contact the Medical Monitor before an emergency breaking of the blind. Reason for unblinding, person conducting the unblinding, personnel who know the unblinded treatment, and date/time of unblinding will be recorded.

12. Study Procedures and Guidelines

[Table 1](#) provides the schedule of assessments depicting the required testing procedures to be performed for the duration of the study. When multiple evaluations are scheduled at the same time point, the priority for each will be as follows:

- At home: For the daily questionnaires that the subject completes at home, the subject should complete the [REDACTED] except on days of study visits when the [REDACTED] will be completed while the subject is at the study site.

- At the clinic:
 - 1) [REDACTED] IGA, EASI, [REDACTED], and Atopic Conditions Questionnaire.
 - 2) Vital signs will be obtained after the subject has been at rest for ≥ 5 minutes.
 - 3) Physical examinations can be performed and urine samples can be collected either before or after other evaluations, unless otherwise specified.

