12.3.2 Pregnancy Test and Follicle-Stimulating Hormone

A serum pregnancy test (hCG level) will be completed for all female subjects of childbearing potential at screening. Women who are surgically sterile (tubal ligation, partial or total hysterectomy, or bilateral oophorectomy) for at least 3 months or those who are postmenopausal for at least 1 year with FSH level >30 mIU/mL are not considered to be of childbearing potential. At screening, FSH levels will be tested on female subjects to confirm postmenopausal status. Both FSH and hCG samples will be processed by the central laboratory.

Subjects with FSH levels ≤ 30 mIU/mL will be considered to be of childbearing potential. Blood will be collected for serum pregnancy test at screening. Urine will be collected for dipstick pregnancy test on all dosing days, Day 8, and all follow-up days (14, 56, and 84 days after last dose of study drug if ET) for all subjects of childbearing potential. Test kits will be supplied by the central laboratory. Tests will be completed on site and evaluated prior to each SC injection. If a subject has a positive pregnancy test, dosing will immediately be discontinued.

To ensure subject safety, each pregnancy in a subject that received study drug must be reported within 24 hours of learning of its occurrence. If the subject received lirentelimab SC, the pregnancy should be followed to determine outcome, including spontaneous or voluntary termination, details of the birth, and the presence of absence of any birth defects, congenital abnormalities, or maternal and/or newborn complications. If the subject received lirentelimab SC, any SAE experienced during pregnancy must be reported on the SAE Report Form.

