14.2 Serious Adverse Events

A SAE is defined as an AE that meets that one of the following criteria:

- Death
- A life-threatening AE that places the subject at risk of death at the time of the event. It does not refer to an event that hypothetically might cause death if it were more severe.
- Inpatient hospitalization or prolongation of existing hospitalization.
- A persistent or significant disability/incapacity.
- A congenital anomaly/birth defect occurring in the offspring of a study subject.
- Other important medical events may also be considered a SAE when, based on appropriate medical judgment, they jeopardize the subject or require intervention to prevent any of the outcomes listed above.

Serious adverse events will be assessed and recorded beginning after the first administration of study drug in the double-blind period and ending at the time of study completion or ET of the

double-blind period or the OLE period, whichever is later. If the SAE is related to a screening procedure, it will be captured from the date of the screening procedure.

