14.8.3 Pregnancy Reporting

Pregnancies are captured if they occur in female subjects or in the sexual partners of male subjects from the time the subject is first exposed to the investigational product and ending at the time of study completion or ET of the double-blind period or the OLE period, whichever is later.

Female subjects must be instructed to discontinue all study drugs and inform the Investigator immediately if they become pregnant during the study. Male subjects must inform the Investigator immediately if their partner becomes pregnant during the study.

The Investigator must report any pregnancy to Allakos within 24 hours of becoming aware of it using the provided pregnancy reporting forms. Female subjects must be immediately discontinued from study drug. An uncomplicated pregnancy will not be considered an AE or SAE, but all pregnancies in subjects who received lirentelimab will be followed through term. For male subjects with female partners who become pregnant, the site will ask the father (the study subject) to provide information about the outcome of the pregnancy and information about the baby. If detailed health information about the mother is requested by Allakos, a Pregnant Partner Information Release Form will be provided to the site for the mother to sign.

Any congenital abnormalities noted at birth in the offspring of a subject who received lirentelimab will be reported as a SAE. If the subject received lirentelimab, the outcome of any pregnancy and the presence or absence of any congenital abnormality will be recorded in the

source documentation and reported to the Medical Monitor and Sponsor via the pregnancy reporting form.

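### Pregnancy follow-up and birth-defect reporting are tied to having received lirentelimab, which contradicts the arm-neutral SAE rules and leaves women treated only with placebo without an explicit route to birth outcomes

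*Protocol*

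**What the plan says.** Two protocol sections attach conditions to what happens after a pregnancy is first reported.

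- Section 12.3.2: "If the subject received lirentelimab SC, the pregnancy should be followed to determine outcome", and "If the subject received lirentelimab SC, any SAE experienced during pregnancy must be reported on the SAE Report Form".
- Section 14.8.3: "all pregnancies in subjects who received lirentelimab will be followed through term"; "Any congenital abnormalities noted at birth in the offspring of a subject who received lirentelimab will be reported as a SAE"; and "If the subject received lirentelimab, the outcome of any pregnancy and the presence or absence of any congenital abnormality will be recorded".

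Other provisions carry no such condition. The first report, due within 24 hours, is required for every pregnancy in a subject given study drug (12.3.2, 14.8.3), and section 10.1 defines study drug as lirentelimab SC and placebo SC together. Section 14.2 lists among the SAE criteria "A congenital anomaly/birth defect occurring in the offspring of a study subject". Section 14.8.2 requires any SAE seen during the study to be reported, attributable or not. For a partner's pregnancy, 14.8.3 has the site ask the father about the outcome and the baby, again with no limit by arm.

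On unblinding, section 11.3 says "Throughout the double-blind study, the blind should remain unbroken except for an emergency" and adds regulatory reporting as a further exception. Section 11.4 gives emergency management and then "if required for regulatory reporting, or if there is a pregnancy during the pregnancy reporting period".

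The SAP plans a listing of pregnancy test results (6.7) and tables of serious TEAEs (6.12.1). It plans no output for pregnancy outcomes.

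**The concern.** Harm should be looked for in the same way in both randomised arms, and the rule for looking should not depend on an allocation that the site does not know. The conditional sentences fail on both counts. The limit is also hard to read as loose wording for study drug, because 12.3.2 uses the defined term for the initial report and then switches to the name of the active product for the later steps.

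At stake is the interpretation of rare events. If one adverse birth outcome is found on lirentelimab because those pregnancies are followed through term, while placebo pregnancies are not explicitly followed that far, there is no equally observed comparator. A site faced with a birth defect in the child of a placebo subject also has two provisions that point in different directions.

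**Working it through.** The plan states no figure on this point. The check sets the provisions side by side, compares the reporting window with the length of a pregnancy, and gives a rough count of events.

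**1. Coverage by arm**

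| Step | Lirentelimab | Placebo only | Source |
|---|---|---|---|
| Initial pregnancy report | Yes | Yes | 12.3.2, 14.8.3 |
| SAE during the study | Yes | Yes | 14.2, 14.8.2 |
| SAE during pregnancy, specific duty | Yes | Not stated | 12.3.2 |
| Pregnancy followed to outcome or term, woman in the study | Yes | Not stated | 12.3.2, 14.8.3 |
| Outcome recorded and sent on the pregnancy form | Yes | Not stated | 14.8.3 |
| Father asked about outcome and baby | Yes | Yes | 14.8.3 |
| Birth defect is an SAE | Yes | Yes under 14.2; left out of 14.8.3 | 14.2, 14.8.3 |

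A placebo subject who is dosed in the open-label extension has then received lirentelimab (Appendix 11) and moves to the first column.

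**2. Does the general SAE rule reach the birth?**

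- SAE recording stops at study completion or early termination (14.2). Without the extension this is about 24 weeks after enrollment, and with it up to 38 weeks (13.13).
- Assumption, not in the documents: a term birth falls 35 to 40 weeks after conception.
- Conception on Day 1 without the extension: 35 - 24 = 11 and 40 - 24 = 16, so the birth comes 11 to 16 weeks after the window closes. Later conceptions are later still.
- With the extension: 38 - 35 = 3, so only conceptions in about the first 3 weeks could reach term inside the window, and everyone in the extension has received lirentelimab.
- Follow-up of unresolved SAEs beyond study exit (14.8.2) does not help, because 14.8.3 does not count an uncomplicated pregnancy as an AE or SAE.

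The general rule therefore covers maternal SAEs, and losses that meet an SAE criterion, during the study in both arms. It reaches practically no term births.

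**3. Expected number of placebo-arm pregnancies in female subjects**

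Inputs: 130 subjects randomised 1:1, so 65 on placebo (protocol 11.2); 24 weeks (13.13); yearly contraceptive failure of 1% to 9%, from the 99% and 91% effectiveness listed for US sites in 12.3.3. The share of women of childbearing potential is not given; 25% to 40% is assumed.

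Expected = 65 x share x (24/52) x yearly failure. P(at least one) = 1 - exp(-expected).

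| Share | Failure | Expected | P(at least one) |
|---|---|---|---|
| 25% | 1% | 0.075 | 7% |
| 25% | 9% | 0.675 | 49% |
| 40% | 1% | 0.12 | 11% |
| 40% | 9% | 1.08 | 66% |

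If every placebo subject entered the extension at Week 14, placebo-only time falls to 14 weeks. The extremes become 0.075 x 14/24 = 0.04 and 1.08 x 14/24 = 0.63, with probabilities of about 4% and 47%. The upper ends are generous: 9% applies only to short-acting hormonal methods in the US list, and the German text requires methods with less than 1% yearly failure.

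**The case against.** The strongest reply is that the conditional sentences add duties for exposed subjects and exempt nobody. Sections 14.2 and 14.8.2 stay in force for placebo subjects, every pregnancy is reported at the outset, and fathers are asked about outcomes in either arm. Nearly all term births fall after the SAE window in both arms, so the serious-TEAE tables would hardly change. Much of this stands. It does not remove the gap in birth outcomes after study exit, and it leaves 14.8.3, the section a site would consult about a birth defect, narrower than 14.2.

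Three stronger readings are tempting, and the documents do not support them.

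- A reader might infer that the placebo arm has no ascertainment of pregnancy harms, or that its pregnancy-related SAE counts are empty by rule. The arm-neutral rows of the coverage table show otherwise.
- A reader might infer that sites must break the blind. Section 11.4 permits unblinding for a pregnancy, and no provision requires it. A site could comply while blinded by following every pregnancy, though the protocol does not say so.
- A reader might infer bias in the primary endpoint: only female subjects are told to stop study drug, so a man unblinded for a partner's pregnancy could go on being scored by an investigator who knows his arm. Section 11.4 leaves this open, but it also lets the Medical Monitor carry out the unblinding and asks for that contact first where possible. The path is hypothetical and nothing in the documents quantifies it.

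**Conclusion.** The point holds as an internal contradiction with a limited consequence. Sections 12.3.2 and 14.8.3 restrict to lirentelimab recipients what 14.2 and 14.8.2 require for everyone, and a blinded site cannot tell which case it has. The practical gap is the birth outcomes of women who received only placebo, once they have left the study.

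The gap is small in numbers: about 0 to 1 placebo-arm pregnancies, with a chance of at least one anywhere from 7% to 66%, and lower with entry to the extension. That range rests on the assumed 25-40% share and on the 1-9% failure rates; the timing argument rests on the assumed 35 to 40 weeks to term. No effect on the primary efficacy result is shown. The change is still worth making, because it concerns equal safety reporting in a randomised comparison and costs very little.

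Separately, 11.3 and 11.4 disagree on whether a pregnancy is a ground for breaking the blind.

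**What to change.** In the conditional sentences of 12.3.2 and 14.8.3, replace *received lirentelimab* (or *lirentelimab SC*) with *received study drug (lirentelimab or placebo)*. This applies to follow-up to outcome or term, SAEs during pregnancy, recording of the outcome, and congenital abnormalities as SAEs. Follow-up and reporting are then the same in both arms, agree with 14.2 and 14.8.2, and need no knowledge of the allocation.

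Sections 11.3 and 11.4 must be reconciled on pregnancy as a ground for unblinding. Which rule should stand is for the sponsor to decide.

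The cost is an amendment to the wording and follow-up to term of roughly 0 to 1 placebo-arm pregnancies on the existing forms.

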14.8.4 AESI Reporting

Beginning from the time of first SC injection of study drug and ending at the time of study completion or ET of the double-blind period or the OLE period, whichever is later, any new AESI (or new information related to a previously reported AESI) must be recorded in the AE eCRF and designated as an “AE of special interest.”

For subjects participating in the OLE period, AESI will be assessed and recorded in the CRF of the AK002-018 double-blind treatment period database up until the start of the first OLE injection after the Day 99 visit and recorded in the CRF of the AK002-018 OLE period database beginning from the start of the first OLE injection after the Day 99 visit.

An AESI that also qualifies as a SAE (per Section 14.2) must also be reported as a SAE in accordance with Section 14.8.2. Adverse events of special interest that are also SAE must be recorded in the AE eCRF and designated as both “serious” and as an “AE of special interest.” These will be reported on the Sponsor-provided SAE forms and should be reported to the Sponsor within 24 hours of site awareness.

14.10 Independent Data Monitoring Committee

An independent Data Monitoring Committee (iDMC) has been convened for this study. The iDMC will meet at established intervals (as per the iDMC charter) throughout the study and will also convene as necessitated by data and/or safety reviews.

14.11 Study Withdrawal Criteria

A subject's participation in the study will be discontinued in the event that:

- Occurrence of an exclusion criterion, which is clinically relevant and affects the subject's safety, if discontinuation is considered necessary by the Investigator and/or Sponsor.
- Rebounding of eosinophil counts to $>1500/\mu\text{L}$ in subjects who entered the study with eosinophil levels $>1500/\mu\text{L}$ and whose eosinophil counts were initially suppressed after study drug, as assessed by the Safety Monitor, may be withdrawn from the study at the instruction of the Medical Monitor.
- Serum transaminases (ALT and/or AST) $>3 \times \text{ULN}$ and total bilirubin $>2 \times \text{ULN}$ (confirmed by repeat) without an alternative explanation.
- Elevation of ALT or AST $>3 \times \text{ULN}$ (confirmed by repeat) with the appearance or worsening of symptoms felt by the Investigator to be potentially related to hepatic inflammation, such as fatigue, nausea, vomiting, right upper quadrant pain or tenderness, fever, and rash.

14.12 Study Stopping Rules

The study may be discontinued prematurely in the event of any of the following:

- A life-threatening AE that is possibly or probably related to treatment.
- A fatal AE that is possibly or probably related to treatment.
- New information leading to unfavorable risk-benefit judgment of the study drug.
- Sponsor's decision that continuation of the study is unjustifiable for medical or ethical reasons.
- Discontinuation of development of the Sponsor's study drug.
- Approval of the national competent authority (i.e. Paul-Ehrlich-Institut or PEI) or the Favorable Opinion/Approval of IEC/IRB for the conduct of the clinical trial is withdrawn.

- The required modification of the maximum insured sum is not possible following a negative change in the assessment of the benefit-risk ratio, if applicable (i.e., for Germany)

Health Authorities and IEC/IRB will be informed about the discontinuation of the study in accordance with applicable regulations. The study may be terminated or suspended on request of Health Authorities or Sponsor.

Study stopping for an individual site or investigator may occur in the event of noncompliance with the protocol or lapse of good clinical practice.

15. Discontinuation and Replacement of Subjects

15.1 Definition of Study Completion

A subject who completes visits through the Day 169 visit will be categorized as having completed the double-blind period of the study.

A subject who completes visits through the Day 99 visit and enters the OLE period of the study will be categorized as having completed the double-blind period of the study.

A subject who completes visits through the OLE Day 169 visit will be categorized as having completed the OLE period of the study.

The study is considered completed when the last subject completes the last study visit.

15.2 Early Discontinuation of Study Drug

A subject may be discontinued from study treatment at any time if the subject, the Investigator, or the Sponsor feels that it is not in the subject's best interest to continue. The following is a list of possible reasons for study treatment discontinuation:

- Subject withdraws consent.
- An AE that in the opinion of the Investigator results in it being in the best interest of the subject to discontinue study treatment.
- Protocol deviation requiring discontinuation of study treatment.
- Participation in any other study during the duration of this study.
- Use of a non-permitted concomitant drug, which may adversely affect data interpretation in the opinion of the Medical Monitor.

- Loss of ability to freely provide consent through imprisonment or involuntary incarceration or treatment of either a psychiatric or physical (e.g., infectious disease) illness.

If a subject is withdrawn from treatment due to an AE, the subject will be followed and treated by the Investigator until the abnormal parameter or symptom has resolved or stabilized.

All subjects who discontinue study drug treatment should be encouraged to continue on study and complete assessments and procedures according to the 12-week follow-up period in [Table 1](#), if possible.

Reasonable attempts will be made by the Investigator to provide reasons for subject withdrawals. The reason for the subject's withdrawal from the study or all attempts to acquire such will be specified in the source documents.

16. Statistical Methods and General Considerations

This section outlines the statistical methods to be used for the analysis of the data from the study. A separate SAP, which must be documented as completed prior to unblinding the study, will describe data handling and statistical techniques in full detail.

Unless specified otherwise, baseline will be defined as the last week of screening before the first SC injection of study drug. All subject data will be listed. When appropriate, summary statistics of number of non-missing values, mean, median, standard deviation, minimum, and maximum will be computed for continuous variables, and summary statistics of number and proportion will be computed for categorical variables. Two-sided 95% confidence intervals (CI) will be provided for the mean and proportion. No formal statistical inferences will be made for safety parameters.

16.1 Sample Size

Approximately 130 evaluable subjects with moderate-to-severe AD will be enrolled. It is hypothesized that the percentage of subjects who achieve EASI-75 at Week 14 are 44% for lirentelimab and 15% for placebo. To detect the treatment difference of 29%, the number of subjects required for 90% power is 55. However, to account for 10% dropout rate, the sample size will be increased to 65 per treatment group.

Enrollment will be monitored to limit the impact of randomizing a disproportionately large number of subjects with an EASI score in the lower range, reflecting more moderate disease only (i.e., EASI score <22). This will also provide a subject population with a full range of EASI scores consistent with the intent to study lirentelimab in moderate-to-severe AD disease.

